10. STUDY AGENT

10.1 Dosing Evaluations

Within 30 days prior to the first scheduled first Therapeutic Dose, subjects will be administered a 3 to 6 mCi Ultratrace iobenguane I 131 Imaging Dose. The imaging dose will be administered based on each subject's body weight. Subjects weighing at least 50 kg will receive 5 to 6 mCi of Ultratrace iobenguane I 131 for imaging. Subjects weighing 30 to 49 kg will receive 0.1 mCi/kg of Ultratrace iobenguane I 131 for imaging, and the Medical Monitor should be consulted for the appropriate imaging dose for subjects weighing less than 30 kg.

Three I 131 whole body scans will be performed to assess tumor uptake and biodistribution, as detailed in Section 11.6 Eligibility/Dosimetry scans. To be eligible to continue in the study, uptake of the study agent by at least one known measurable tumor on the Image 2 or Image 3 scan must be documented. Images 1, 2 or 3 will be evaluated centrally to confirm tumor uptake and biodistribution. The dosimetry study will be performed using these three Images. This will ensure that even a single dose of 500 mCi does not result in an absorbed dose exceeding 23 Gy to the kidney, 17.5 Gy to the lungs and 30 Gy to the liver. These limits are based upon the Emami Criteria.⁴⁴ Should the dosimetry study show that a reduction in the activity of Ultratrace iobenguane I 131 is warranted, both Therapeutic Doses to be administered will be equally adjusted to specified dose levels (see Section 10.2).

Approximately three months following the initial Therapeutic Dose of Ultratrace iobenguane I 131, the subject will be administered the second Therapeutic Dose. The hematological laboratory values must be reviewed by the Principal Investigator and MIP prior to administration of the second Ultratrace iobenguane I 131 for any subject. The determination whether to proceed with the second Therapeutic Dose of Ultratrace iobenguane I 131 will be made based on the hematological status following the first therapy dose. The dosimetry calculation done prior to the first therapeutic dose must demonstrate that the cumulative absorbed dose does not exceed specified absorbed dose levels for the specified organs. Additionally, the subject's hematological laboratory values must demonstrate full recovery to the normal range or the subject's baseline following the first dose of Ultratrace iobenguane I 131. If after the first dose of Ultratrace iobenguane I 131, the subject experiences any of the following hematological toxicities:

- Febrile neutropenia (temperature \geq 38.5° C and ANC <1,000/µL); or
- CTCAE Grade 3 thrombocytopenia with active bleeding; or
- CTCAE Grade 4 hematological toxicity >1 week duration;

Then the subject's hematological laboratory values must return to baseline before receiving the second dose of Ultratrace iobenguane I 131. Additionally, any subject who experiences a hematologic toxicity as described above must receive a decreased second dose, as described in Section 10.2.

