10.2 Dose Modification

Dosimetry will be calculated to confirm that the protocol-specified two administrations of 500 mCi (or 8 mCi/kg for subjects weighing 62.5 kg or less) of Ultratrace iobenguane I 131 does not exceed the specified absorbed dose levels (23 Gy to the kidney, 17.5 Gy to the lungs and 30 Gy
to the liver) over the entire treatment (two therapeutic doses). Additionally, subjects must have recovered from treatment side effects experienced during the initial dose and prior to administration of the second dose. Dose modification, if required, may be based on subject's body weight, estimated renal, hepatic or lung absorbed dose or hematological toxicity. Similarly, the Principal Investigator or designee may modify second dose scheduling, in consultation with the study medical monitor, due to medical condition and/or other logistic or personal reasons. In any case this delay of second therapeutic dose should not exceed 24 weeks from the first therapeutic dose. Specifically, if the total dose requires downward adjustment resulting from the dosimetry calculation, then both the first and second Treatment Doses will be decreased equally.

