10.2.2 Dose modification for hematologic toxicity

The subject's hematologic values must return to baseline levels prior to administration of the second Therapeutic Dose. The administration of the second Therapeutic Dose may be delayed for up to 4 - 12 weeks (i.e., 16 - 24 weeks following administration of the first Therapeutic Dose) to allow for adequate hematologic recovery. If recovery to baseline levels has not occurred within 24 weeks following the initial Therapeutic Dose, the subject should be discontinued from the study.

Additionally, if the subject has experienced:

- Febrile neutropenia (temperature \geq 38.5° C and ANC <1,000/µL); or
- CTCAE Grade 3 thrombocytopenia with active bleeding; or
- CTCAE Grade 4 hematological toxicity >1 week duration at any time following administration of the initial Therapeutic Dose,

The second Therapeutic Dose should be decreased to 425 mCi (or 7 mCi/kg for subjects weighing less than 62.5 kg).

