7.4.1. Primary Analysis: Reduction in Use of Antihypertensive Medication

The primary endpoint for this trial is the proportion of study subjects with a reduction (including discontinuation) of all antihypertensive medication by at least 50% for at least six months or two cycles of iobenguane I 131. The 50% reduction is determined separately for each baseline medication, based on the total daily dose of the antihypertensive medication(s) on the day of the first therapeutic dose.

A benefit duration period is measured by maximum duration as follows. The benefit duration period commences when the subject's medication is reduced to a level below 50% of baseline, and continues until the subject's medication rises above 50% of baseline, until the onset of a new antihypertensive medication of >14 days' duration, or to the last subject date as described in section 7.4.2, Primary Endpoint Calculation. A benefit duration period must begin during the 12-Month Efficacy Phase but may end during the Long-term Follow-up Phase. If the subject discontinues participation in the study before the Month 12 efficacy evaluation, the last date for calculation of the duration of benefit is the date of termination in the study.

For purposes of illustration, the following examples are provided (Month refers to the number of 28-day months after the first Therapeutic Dose).

- Example 1: A subject experiences the clinical benefit from the beginning of Month 2 to the beginning of Month 4, and then again from the beginning of Month 5 to the beginning of Month 12. Since the maximum duration of the benefit was 7 months, the subject is considered a success on the primary endpoint.
- Example 2: A subject experiences the clinical benefit from the beginning of Month 2 to the beginning of Month 4, and then again from the beginning of Month 6 to the beginning of

Month 11. Even though the subject experienced the clinical benefit for a total of 7 months, the maximum duration of the benefit was only 5 months, so the subject is considered a failure on the primary endpoint.

- Example 3: A subject experiences the benefit from the beginning of Month 2 to the beginning of Month 9. At Month 10, the subject receives another anticancer treatment and is discontinued from the study. Since the maximum duration of the benefit was 7 months, prior to discontinuation, the subject is considered a success on the primary endpoint.

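### Protocol 10.1 and 10.2.2 give opposite answers on the second Therapeutic Dose for subjects with no listed toxicity whose counts are normal but not back to baseline

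*Protocol*

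**What the plan says.** Protocol 10.1 sets a general condition for the second Therapeutic Dose: "the subject's hematological laboratory values must demonstrate full recovery to the normal range or the subject's baseline following the first dose". It then lists three toxicities: febrile neutropenia, Grade 3 thrombocytopenia with active bleeding, and Grade 4 hematological toxicity lasting more than one week. For subjects who had one of these it adds a stricter condition: "Then the subject's hematological laboratory values must return to baseline before receiving the second dose of Ultratrace iobenguane I 131". It also requires the investigator and the sponsor to review the hematological values of every subject before the second dose.

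Protocol 10.2 says only that "subjects must have recovered from treatment side effects experienced during the initial dose and prior to administration of the second dose", with no level stated.

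Protocol 10.2.2 opens with an unconditional rule: "The subject's hematologic values must return to baseline levels prior to administration of the second Therapeutic Dose". It allows a delay to 16–24 weeks after the first dose and continues: "If recovery to baseline levels has not occurred within 24 weeks following the initial Therapeutic Dose, the subject should be discontinued from the study". The same three toxicities come afterwards, introduced by "Additionally, if the subject has experienced", and there they trigger only the decreased second dose.

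On the analysis side, Protocol 13.1 and SAP 5.4 exclude subjects with only one Therapeutic Dose from the Per Protocol Set. SAP 7.4.1 says that for a subject who discontinues before the Month 12 evaluation, "the last date for calculation of the duration of benefit is the date of termination in the study".

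**The concern.** Two rules in the current protocol can be applied to the same blood counts with different results. One permits the second dose. The other withholds it and, at 24 weeks, takes the subject off study. Section 10.1's separate baseline rule for the three toxicities has a purpose only if the normal range is enough for everyone else, and the unconditional sentence in 10.2.2 removes that distinction.

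Three things are at stake.

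- **Exposure:** one dose or two. SAP 7.8 also uses the number of doses as a subgroup factor.
- **Per Protocol membership:** a subject held back under 10.2.2 leaves the set. A subject dosed under 10.1 might be recorded as a deviation from 10.2.2. Protocol 13.2 plans for 58 subjects in this set.
- **Possibly the primary endpoint:** this depends on whether a discontinuation under 10.2.2 closes the benefit period.

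**Working it through.** The documents give no figure to reproduce, so the check is a comparison of the rules case by case, followed by the timing arithmetic for the primary endpoint.

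**Step 1. Apply both sections to each case.**

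| Counts before dose 2 | Listed toxicity? | 10.1 | 10.2.2 | Conflict |
|---|---|---|---|---|
| Back to baseline | Either | Dose 2 allowed | Dose 2 allowed | No |
| Neither normal nor at baseline | Either | Not allowed | Not allowed | No |
| Normal, not at baseline | Yes | Not allowed (baseline required) | Not allowed | No |
| Normal, not at baseline | No | Dose 2 allowed | Delayed; should be discontinued if not at baseline within 24 weeks | **Yes** |

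The table concerns recovery only. The reduced second dose after a listed toxicity is the same requirement in both sections.

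**Step 2. Does anything else in the text settle the last row?** The heading of 10.2.2 refers to toxicity, but its baseline sentence is unconditional and precedes the toxicity list. The wording in 10.2 names no level. The sponsor review in 10.1 says who looks at the values, not which criterion they apply. The conflict therefore remains.

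**Step 3. Per Protocol Set.** Two doses are required, so in the last row 10.1 can keep a subject in the set while 10.2.2 removes the same subject. This follows directly from Protocol 13.1 and SAP 5.4.

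**Step 4. Primary endpoint timing.** SAP 7 defines a month as 28 days for this endpoint, so six months is 6 × 28 = 168 days, as SAP 7.4.2 states. The 24-week limit is 24 × 7 = 168 days. The latest day on which a benefit period can start and still reach 168 days is the termination day minus 168:

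- Termination recorded exactly at Day 168: 168 − 168 = Day 0, the day of dose 1.
- Termination recorded in the Month 6 window of Protocol 11.5.18 (Day 173–193): 173 − 168 = Day 5, to 193 − 168 = Day 25.
- Discontinuation under 10.2.2 not treated as termination: no cut at this point, and the benefit period may start at any time in the 12-month efficacy phase.

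**Step 5. Which of these applies?** SAP 7.4.1's general sentence points to a cut. SAP 7.4.2 attaches its early end date to six reasons: withdrawn consent, loss to follow-up, death, progressive disease, other anticancer therapy, and an adverse event resulting in discontinuation. Failure to regain baseline is not among them, nor is it among the criteria in Protocol 9.7. Protocol 9.8 says discontinued subjects who have not withdrawn consent should continue scheduled assessments other than CT, MR and bone scans and tumor markers. The documents do not decide between the lines in Step 4.

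**The case against.** The strongest reply is that this is a narrow wording difference with little effect on the main result. The primary analysis uses the Full Analysis Set, and SAP 7.4.2 lets a subject respond after a single Therapeutic Dose. The Per Protocol analysis is secondary. Every case passes a sponsor review before dose 2, and SAP 5.4 already provides a deviation review before lock. Under 10.2.2 the first consequence is delay, not discontinuation. Protocol 7.3 reports that in the dose-escalation study counts returned to pre-treatment values by 8 weeks, so few subjects may still be short of baseline at 24 weeks. A protocol clarification can also hardly change dosing once enrollment has closed.

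Most of this stands, and it limits the size of the point. It does not remove the conflict: a common review without a stated criterion cannot show which rule was applied, and the deviation review cannot classify these subjects consistently while two rules are in force.

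A reader might infer something stronger: that each such subject must be off study by Day 168 and is therefore an almost certain non-responder. On that view, at the design alternative of 0.25, every 1 / 0.25 = 4 such subjects would cost about one expected responder. The documents do not support this. The rule takes effect once 24 weeks have passed without recovery, it says should rather than must, and the benefit cut is unsettled (Step 5). The response rate in this group is also unknown; at the null value of 0.10 the same arithmetic gives 1 / 0.10 = 10 subjects per responder. A reader might also take 10.1 as accepting the normal range for everyone. It does not, because it requires baseline after a listed toxicity.

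**Conclusion.** The contradiction is real and stands in the current text, but it is confined to subjects without a listed toxicity whose counts are normal and not back to baseline. For them the choice of section decides second-dose exposure and Per Protocol membership. An effect on the primary endpoint is possible but not established: it depends on treating a discontinuation under 10.2.2 as study termination, which SAP 7.4.1 suggests and SAP 7.4.2 and Protocol 9.8 leave open. The number of subjects affected is not given, so no size can be computed for any of these effects. The conclusion rests on reading the first sentence of 10.2.2 as unconditional, which is how it is written. No view is taken on which recovery rule is right.

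**What to change.** 1. Reconcile Protocol 10.1 and 10.2.2 into one recovery criterion, stated once and cross-referenced. The choice belongs to the sponsor and its clinical advisers.
2. SAP 4.1 records that enrollment was completed in December 2015, so a text change alone may come too late to affect dosing. Before database lock, list the subjects without a listed toxicity who were dosed, delayed or discontinued with counts in the normal range but not at baseline. Note which wording was applied to each.
3. Record their Per Protocol classification in the addendum that SAP 5.4 already calls for.
4. State in SAP 7.4.2 whether a discontinuation under Protocol 10.2.2 ends the benefit period and, if so, on which date.

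The cost is a short protocol clarification, one sentence in the SAP, and a review of hematology and dosing records already collected. No new data are needed.

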10.2 Dose Modification

Dosimetry will be calculated to confirm that the protocol-specified two administrations of 500 mCi (or 8 mCi/kg for subjects weighing 62.5 kg or less) of Ultratrace iobenguane I 131 does not exceed the specified absorbed dose levels (23 Gy to the kidney, 17.5 Gy to the lungs and 30 Gy
to the liver) over the entire treatment (two therapeutic doses). Additionally, subjects must have recovered from treatment side effects experienced during the initial dose and prior to administration of the second dose. Dose modification, if required, may be based on subject's body weight, estimated renal, hepatic or lung absorbed dose or hematological toxicity. Similarly, the Principal Investigator or designee may modify second dose scheduling, in consultation with the study medical monitor, due to medical condition and/or other logistic or personal reasons. In any case this delay of second therapeutic dose should not exceed 24 weeks from the first therapeutic dose. Specifically, if the total dose requires downward adjustment resulting from the dosimetry calculation, then both the first and second Treatment Doses will be decreased equally.

10.2.1 Dose modification due to renal, lung or liver absorbed exposure

The calculated cumulative dose for the study must be confirmed not to exceed 23 Gy exposure to the kidneys, 30 Gy to the liver, and 17.5 Gy to the lungs. If based on CT or MRI, the target organ does not contain tumor, then the dose will be decreased in a proportional fashion to fall below the theoretical organ tolerance. Should the organ estimate include tumor tissue, then a separate region of interest for 'non-involved' normal organ tissue will be computed and extrapolated to an equivalent total organ radiation dose assuming no internalized tumors. This radiation dose estimate represents the best estimate of the radiation dose to the 'non-involved' organ tissue and should be applied to the normal organ toxicity limits established. If this value exceeds the radiation limits, then the administered activity will be reduced proportionally to achieve an estimated normal organ total radiation dose per the limiting value. If the organ is diffusely infiltrated with tumor or contains large extensive metastatic lesions, then this will require careful review of the scans and dosimetry by the responsible dosimetrist, Principal Investigator and study medical monitor to determine the most accurate and safe dose adjustment. Whenever a dose adjustment is warranted, all scheduled doses will be adjusted equally.

10.2.2 Dose modification for hematologic toxicity

The subject's hematologic values must return to baseline levels prior to administration of the second Therapeutic Dose. The administration of the second Therapeutic Dose may be delayed for up to 4 - 12 weeks (i.e., 16 - 24 weeks following administration of the first Therapeutic Dose) to allow for adequate hematologic recovery. If recovery to baseline levels has not occurred within 24 weeks following the initial Therapeutic Dose, the subject should be discontinued from the study.

Additionally, if the subject has experienced:

- Febrile neutropenia (temperature \geq 38.5° C and ANC <1,000/µL); or
- CTCAE Grade 3 thrombocytopenia with active bleeding; or
- CTCAE Grade 4 hematological toxicity >1 week duration at any time following administration of the initial Therapeutic Dose,

The second Therapeutic Dose should be decreased to 425 mCi (or 7 mCi/kg for subjects weighing less than 62.5 kg).

10.3 Study Agent Description

10.3.1 Ultratrace Iobenguane I 131

Each vial of Ultratrace iobenguane I 131 consists of a sterile, clear aqueous solution. The dose is provided in a glass vial capped with a gray septum and aluminum crimp. The primary container is shipped in a secondary lead shield container, to limit exposure. The Dosimetry and therapy doses are shipped frozen on dry ice. The product for both the imaging Ultratrace iobenguane I 131 and the therapy Ultratrace iobenguane I 131 will have the same formulation but a lower total radioactivity and radioactive concentration will be used for imaging. Excipients include ascorbic acid and gentisic acids. Please refer to the Investigator Brochure for a more complete description of the formulation. Radioactivity values are at Time of Calibration (TOC), see the Pharmacy Manual for further information. The Time of Expiration is eight days post manufacture. The drug should be stored at \leq -70°C with adequate shielding (e.g., lead pot, lead bricks, etc.).

10.4 Receipt and Storage of Drug Product

The storage condition and expiration of the Ultratrace iobenguane I 131 product are described in the Pharmacy Manual and must be strictly followed. The drug product contains radioactive material and should only be handled by personnel trained in the use of radioactive isotopes with proper shielding and monitoring. Receipt and use of the drug product is limited to a facility licensed by the Federal or State authorities. Unused or residual waste should be disposed of as radioactive waste following the institution's standard operating procedures (SOPs) and/or applicable regulations or guidances.

10.5 Blinding and Randomization

This is an open-label, single arm study.

10.6 Handling and Preparation

Ultratrace iobenguane I 131 must be handled according to hospital policy for radioactive diagnostic isotopes. The Imaging and Therapeutic Ultratrace iobenguane I 131 must be used within the expiration dates as outlined in Section 10.3.1. The appropriate temperature and storage conditions will be further described in the Azedra Pharmacy Manual.

The contents are sterile and aseptic procedures should be employed during the withdrawal of doses for administration.

Care should be taken to equalize the pressure in the syringe and vial when drawing the drug from the vial. Use of a vent needle is recommended.

10.7 Administration

Before administration of Ultratrace iobenguane I-131, the subject's thyroid should be blocked with inorganic iodine. The site may use an institutionally approved thyroid blocking protocol or utilize the following recommendations adopted from the CDER potassium iodide thyroid blocking agent guidance.

The administration of potassium iodide should begin 24 hours prior to the administration of Ultratrace iobenguane I-131 and should continue for a total of 10 days. Children ages 12 through 18 years should receive 65 mg potassium iodide daily for a 10 day course of therapy. Adolescents approaching adult size (greater than or equal to 70 kg) should receive the full adult dose. Adults 18 years and older, should receive potassium iodide 130mg daily for a 10 day course of therapy. Potassium iodide can be diluted in milk, infant formula, juice or water. The product can be taken with food to minimize gastric irritation.

There are several commercially available products such as:

- Potassium iodide (SSKI 1gm/ml): 50-250 mg (1-5 drops SSKI), 1 drop = 50 mg (contains sodium thiosulfate)
- Lugol's solution: potassium iodide (100 mg/ml)
- Pima syrup: 325 mg/5ml (black raspberry flavor)
- ThyroShield: 65 mg/ml (30 ml black raspberry flavor)
- Iosat: 130mg tablet
- ThyroSafe: 65 mg tablet (equivalent to iodine 50mg)

To minimize irradiation of the urinary bladder, the subject should be encouraged to increase fluid intake and to void frequently through the first day after administration.

Prophylactic antiemetic therapy is recommended prior to the administration of therapeutic Ultratrace iobenguane I 131 to reduce or eliminate nausea and vomiting. Investigators may use the antiemetic guidelines as prescribed by their institution, typically starting the day of therapeutic Ultratrace iobenguane I 131 administration and continuing 2-5 days, depending upon the subject's antiemetic history and Investigator's evaluation.

Salivary gland stimulation should be encouraged for subjects in order to prevent or decrease the possibility of radiation sialadenitis. Subjects may be advised to hydrate well by ingesting at least 2 liters of liquid per day and stimulate salivation by chewing gum or sucking hard candy (sour candy with citric acid or equivalent is best) while awake for one week following Ultratrace iobenguane I 131 therapy.

Careful attention to hydration status, particularly in the setting of gastrointestinal intolerability is required. Ensuring optimal hydration status before therapy is an important component of subject preparation.

Prior to Ultratrace iobenguane I 131 imaging injection, an indwelling intravenous catheter will be inserted into the antecubital vein (or an equivalent venous access). The radiopharmaceutical will be injected through the indwelling catheter. The Imaging Dose will be administered slowly over a period of approximately 60 seconds.

The first Therapeutic Dose of Ultratrace iobenguane I 131 will be administered after the dosimetry calculations are complete. The first therapeutic infusion may be administered up to 30 days after the Imaging dose if subject scheduling or product availability causes a delay in therapy.

The subject will be weighed before the Therapeutic Dose is drawn. If the subject's weight has changed by more than ± 2 kg since the calculation of the Therapeutic Dose of Ultratrace iobenguane I 131, the dose will be recalculated.

Please refer to the Ultratrace iobenguane I 131 Therapeutic Dose Infusion System Clinical Manual and the Pharmacy Manual when preparing and administering a therapeutic dose. Both manuals provide recommendations for the preparation and administration of the drug that may be modified in accordance with each institution's standard operating procedures. The recommended infusion rate of the Therapeutic Dose is 50 mL over a period of 15 to 60 minutes. At infusion intervals that are less than 30 minutes, some patients receiving the infusion via peripheral venous access have reported infusion site discomfort. Therefore, MIP recommends a peripheral infusion rate of less than or equal to 50 mL over 30 minutes (100 mL/hour). If needed, infusion site discomfort may be managed by slower infusion rates or by stopping the infusion temporarily. Ultratrace iobenguane I 131 Therapeutic Dose Infusion System Clinical Manual can be consulted for further details.

Following completion of each administration (imaging or therapy) of Ultratrace iobenguane I 131, 10 mL of normal saline will be delivered through the catheter.

An interruption in a therapeutic infusion is allowed to accommodate subject issues (e.g., toilet, nausea, vomiting, anxiety, etc.). Most of these are avoidable by good subject education and dose planning. The subject's infusion should not be discontinued unless the Investigator determines that continuing would represent an unacceptable risk, undue safety hazard, or if subject's medical condition deteriorates rapidly and the infusion cannot continue or would interfere with medical or surgical care. As long as infusion is expected to finish on the day scheduled, it may proceed even with interruptions.

Investigators will be made aware that a theoretical risk for hypertensive crisis, most commonly seen after hepatic embolization, cannot be excluded after therapeutic Ultratrace iobenguane I 131 infusion. Phentolamine or other acute therapeutic measures and physicians trained in managing hypertensive crisis or severe cardiovascular adverse events should be readily available during each infusion.

Any misadministration of any infusion (e.g., overdose, observable extravasation, medication error) will be recorded in the subject's source records and transcribed onto the case report form (CRF) and reported within 24 hours using the SAE form for initial communication. Therapeutic over dosage or under dosage may also require a separate report to the competent regulatory authority governing the use of medical radioactive material.

Investigators will follow radiological isolation procedures after the therapeutic dose of Ultratrace iobenguane I 131 as governed by institutional and local radiological authorities.

